11.6 Identification of Legally Authorized Representatives

Many of the patients approached for participation in this research protocol will have impaired decision-making capacity due to critical illness and will not be able to provide informed consent. Accordingly, informed consent will be sought from the patient's LAR.

Regarding consent from the LAR, the existing federal research regulations ('the Common Rule') states at 45 CFR 46.116 that "no investigator may involve a human being as a subject in research...unless the investigator

has obtained the legally effective informed consent of the subject or the subject's legally authorized representative"; and defines at 45 CFR 46 102 (c) a LAR as "an individual or judicial or other body authorized under applicable law to consent on behalf of a prospective subject to the subject's participation in the procedures(s) involved in the research." The Office of Human Research Protections (OHRP) defined examples of "applicable law" as being state statutes, regulations, case law, or formal opinion of a State Attorney General that addresses the issue of surrogate consent to medical procedures. Such "applicable law" could then be considered as empowering the LAR to provide consent for participant participation in the research. Interpretation of "applicable law" may be state specific and will be addressed by the central IRB.

According to a previous President's Bioethics Committee (National Bioethics Advisory Committee (NBAC)), an investigator should accept a relative or friend of the potential participant who is recognized as an LAR for purposes of clinical decision making under the law of the state where the research takes place.⁴⁶ Finally, OHRP has stated in their determination letters that a surrogate could serve as a LAR for research decision making if such an individual is authorized under applicable state law to provide consent for the "procedures" involved in the research study

11.7 Justification of Surrogate Consent

According to the Belmont Report, respect for persons incorporates at least two ethical convictions; first, that individuals should be treated as autonomous agents, and second, that persons with diminished autonomy are entitled to protection. One method that serves to protect patients is restrictions on the participation of patients in research that presents greater than minimal risk. Commentators and research ethics commissions have held the view that it is permissible to include incapable participants in greater than minimal risk research as long as there is the potential for beneficial effects and that the research presents a balance of risks and expected direct benefits similar to that available in the clinical setting.⁴⁷ Several U.S. task forces have deemed it permissible to include incapable participants in research. For example, the American College of Physicians' document allows surrogates to consent to research involving incapable participants only "if the net additional risks of participation are not substantially greater than the risks of standard treatment".⁴⁸ Finally, NBAC stated that an IRB may approve a protocol that presents greater than minimal risk but offers the prospect of direct medical benefits to the participant, provided that "the potential subject's LAR gives permission...".⁴⁶

Consistent with the above ethical sensibilities regarding the participation of decisionally incapable participant in research and the previous assessment of risks and benefits in the previous section, the present trial presents a balance of risks and potential direct benefits that is similar to that available in the clinical setting.

11.8 Additional Safeguards for Vulnerable Participants

The present research will involve participants who might be vulnerable to coercion or undue influence. As required in 45CFR46.111(b), we recommend that sites utilize additional safeguards to protect the rights and welfare of these participants. Such safeguards might include but are not limited to a) assessment of the potential participant's capacity to provide informed consent, and b) the availability of the LAR to monitor the participant's subsequent participation and withdrawal from the study. The specific nature of the additional safeguards will be left to the discretion of the central IRB, in conjunction with the sites.

11.9 Confidentiality

Federal regulations at 45 CFR 46 111 (a) (7) requires that when appropriate, there are adequate provisions to protect the privacy of participants and to maintain the confidentiality of data. At no time during this study, its analysis, or its publication will patient identities be revealed in any manner. The minimum necessary data containing patient or provider identities will be collected. All patients will be assigned a unique study ID number for tracking. All data collected for this study will be entered directly into a secure online database. All data will be maintained in the secure online database until the time of study publication. At the time of publication, a de-identified version of the database will be generated. Further, tools within the secure online database will be used so that only the VCC and investigators from the enrolling site will have access to data from participants enrolled at that site.

12. ADVERSE EVENTS

Assuring patient safety is an essential component of this protocol. Convalescent plasma has been approved by the Food and Drug Administration and used in clinical practice for decades with an established safety profile. Use of convalescent plasma for the treatment of acute respiratory infection due to COVID-19, however, raises unique safety considerations. This protocol addresses these considerations including the following:

1. Exclusion criteria designed to prevent enrollment of patients likely to experience adverse events with receipt of convalescent plasma
2. Inpatient monitoring of the patient by bedside nurses during and after infusion of the plasma
3. Proactive education of treating clinicians regarding relevant adverse reactions to convalescent plasma
4. On-study monitoring of co-interventions (e.g., medications) and patient characteristic to help prevent adverse events
5. Systematic collection of safety outcomes relevant to use of convalescent plasma
6. Structured reporting of adverse events

12.1 Adverse Event Definitions

Adverse Event: Any untoward medical occurrence associated with the use of an infusion or a study procedure, whether or not considered infusion related.

Serious Adverse Event: Adverse events that are serious as defined in section 12.2 below.

Adverse Reaction: An adverse reaction means any adverse event caused by a study intervention. An adverse reaction is a subset of all suspected adverse events where there is a reason to conclude that the study intervention caused the event.

Suspected Adverse Reaction: Any adverse event for which there is a reasonable possibility that the study procedures caused the adverse event. Reasonable possibility means there is evidence to suggest a causal relationship between the study procedures and the adverse event. A suspected adverse reaction implies a lesser degree of certainty about causality than adverse reaction.

Suspected Unexpected Serious Adverse Reaction (SUSAR): An adverse reaction that is both unexpected (not consistent with risks outlined in the study protocol or investigator brochure), serious, and meets the definition of a suspected adverse reaction.

12.2 Serious Adverse Events

Serious adverse event collection begins after randomization and study procedures have been initiated. If a patient experiences a serious adverse event after consent, but prior to randomization or starting study procedures, the event will NOT be collected. Study site personnel must alert the VCC, via data entry in the adverse event case report form, of any **serious and study procedure related** adverse event within 24 hours of investigator awareness of the event. If a serious adverse event is communicated to the VCC via telephone, it should be immediately followed with official notification on the adverse event case report form.

As per the FDA and NIH definitions, a serious adverse event is any adverse event that results in one of the following outcomes:

- Death
- A life-threatening experience (that is, immediate risk of dying)
- Prolonged inpatient hospitalization or re-hospitalization
- Persistent or significant disability/incapacity

As per <http://www.fda.gov/Safety/MedWatch/HowToReport/ucm053087.htm>: Report an adverse event as serious if admission to the hospital or prolongation of hospitalization was a result of the adverse event. Emergency department visits that do not result in admission to the hospital should be evaluated for one of the other serious outcomes (e.g., life-threatening; required intervention to prevent permanent impairment or damage; other serious medically important event).

As per <http://www.fda.gov/Safety/MedWatch/HowToReport/ucm053087.htm>: Report an adverse event serious if the adverse event resulted in a substantial disruption of a person's ability to conduct normal life functions, i.e., the adverse event resulted in a significant, persistent or permanent change, impairment, damage or disruption in the patient's body function/structure, physical activities and/or quality of life.

Adverse events that may not result in death, be life-threatening, or require hospitalization may be considered serious adverse events when, based upon appropriate medical judgment, they jeopardize the patient and may require medical or surgical intervention to prevent one of the outcomes listed in this definition.

Serious adverse events will be collected **through study day 4**, 72 hours after completion of the study infusion, or until hospital discharge, whichever occurs first, regardless of the investigator's opinion of causation.

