5. STUDY INTERVENTIONS

5.1 Treatment of Study Participants

A summary of the trial's schedule of events is included in Appendix A.

Timing of study procedures is based on the time of initiation of the study product infusion, which is defined as "Time 0". Study Day 1 is defined as the calendar day of study product infusion. For patients who are randomized but do not receive study product, time of randomization will be considered "Time 0" and Study 1 will be the calendar day of randomization. For most patients, randomization and study product infusion will occur on the same day; in the event the study product is infused on a different calendar day than randomization, Study Day 1 is defined as the day on which study product is infused. "Baseline status" represents the patient's status immediately prior to study infusion, and baseline variables should represent information available before and as close as possible to initiation of the study infusion. The primary outcome will be assessed on Study Day 15 which corresponds to 2 weeks (14 days) after the receipt of the study infusion.

Transfusion of convalescent plasma or placebo will be administered as a single dose by clinical or research personnel while the patient is hospitalized and within 24 hours of randomization. Participants randomized to active treatment will receive 1 unit of convalescent plasma, which has a volume of 200-399 ml infused intravenously. Patients randomized to placebo will receive 250 ml of lactated Ringer's with multivitamin additives infused intravenously. The duration of infusion is recommended to be between approximately 1 hour and 3 hours (at the discretion of the provider), with the specific rate of infusion determined by the site investigator based on an assessment of how quickly the participant can safely receive the intravascular volume load.

Study personnel will monitor patients for adverse reactions to the transfusion while the patient is in the hospital for 72 hours following the infusion; that is transfusion adverse reaction monitoring will be continued until Study

Day 4. For patients who are discharged prior to Day 4, study personnel will obtain safety outcomes from the patient or surrogate via telephone follow-up scheduled at Day 8. Research personnel will also assess patients at Day 15 and Day 29; these assessments will be completed by phone if the patient has been discharged from the hospital.

Screening, consent, and baseline

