12.3 Safety Monitoring

Assuring patient safety is an essential component of this protocol. Each participating investigator has primary responsibility for the safety of the individual participants under his or her care. The investigators will determine daily if any adverse events occur during the period from enrollment through **study day 4,(which is** 72 hours after completion of the study product infusion, or hospital discharge, whichever occurs first, and will determine if adverse events are related to study procedures. Adverse events are not required to be reported to the IRB unless the investigator feels the adverse event **was related** to study infusion or study procedures.

The following adverse events will be collected in the adverse event case report forms:

- Serious adverse events (as defined in protocol section 12.2 of this protocol) that are study related (or of uncertain relationship) or occur within 72 hours of the study infusion
- Non-serious adverse events that are study procedures or of uncertain relationship
- Events leading to permanent discontinuation of study infusion (which, by definition, are study related)

The protocol for reporting adverse events in the trial's electronic data capture system are summarized in Table 4.

Table 4. Protocol for reporting adverse events

Type of Adverse Event	Time for Recording in the EDC
Serious, study related	24 hours
Serious, not study related and within 72 hours of infusion	72 hours
Serious, not study related and after 72 hours following	Recording in the EDC is not required
Not serious, study related	72 hours
Not serious, not study related	Recording in the EDC is not required

Study-specific clinical outcomes (Primary, Secondary and Safety Outcomes and Assessments During the Study), including serious outcomes such as organ failures and death, are systematically recorded in the case report forms and are exempt from adverse event reporting unless the investigator deems the event to be related to the administration of study plasma or the conduct of study procedures (or of uncertain relationship).

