Appendix A: Schedule of Events

	Screening & Consent	Baseline & Transfusion	Follow-up									
			2	3	4	5	6	7	8 ¹	15 ¹	29 ¹	
Day	1 or before	1										
Confirm eligibility, including positive SARS-CoV-2 test	x											
Informed consent	x											
Randomization		x										
Demographic and Medical history		x										
ABO type (complete on study protocol if clinical results not available; follow institutional policy)		x ⁴										
Study infusion		x ²										
Record vital signs		x	x ³	x ³	x ³	x ³	x ³	x ³	x ³			
COVID-19 symptom screen		x										
Concomitant medications		x										
Assessment with COVID-19 7-point Ordinal Clinical Progression Outcomes Scale		x	x ³	x ³	x ³	x ³	x ³	x ³	x	x	x	
Collect data for later calculation of SOFA score		x	x ³									
Record new medical conditions		x	x ³	x ³	x ³	x ³	x ³	x ³	x	x	x	
Adverse event monitoring		x	x ³	x ³	x ³							
CRP (complete on study protocol if clinical results not available)		x ⁴										
CBC and CMP (complete on study protocol if clinical results not available)		x ⁴	x ^{3,4}									
Blood for COVID-19 titer testing		x ⁵	x ³									
Record the results of a clinically obtained CBC and CMP (only if clinically available)									x			

¹ If patient is discharged before the follow-up visits on Day 8, 15, and 29, follow-up study activities on these days will be performed via phone calls. Day 8 call window will be Day 8 through 14. The Day 15 call window will be Day 15 through 22. The Day 29 call window will be Day 29 through 36

² Study infusion will be monitored per site institutional transfusion policy.

³ Only performed if hospitalized.

⁴ Only if not performed as part of standard of care.

⁵ Must be drawn prior to study infusion.

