Appendix B: Adverse Event Reporting and Unanticipated Events

Investigators will report all serious adverse events that occur within 72 hours of study infusion to the Vanderbilt Coordinating Center (VCC) regardless of relatedness. Serious adverse events that are determined to be related to study procedures (regardless of timing related to study infusion) will be reported to the VCC within 24 hours. Hence, all serious adverse events judged to be related or possibly related to study procedures will be reported within 24 hours (Figure 2). The VCC will then notify the single Institutional Review Board (sIRB).

The Medical Monitor will work collaboratively with the reporting investigator to determine if a serious adverse event has a reasonable possibility of having been caused by the study infusion or study procedure, as outlined in 21 CFR 312.32(a)(1), and below. The Medical Monitor will be unblinded and will also determine if the event is unexpected for convalescent plasma. An adverse event is considered “unexpected” if it is not listed in the investigator brochure or the study protocol [21 CFR 312.32(a)]. If a determination is made that a serious adverse event has a reasonable possibility of having been caused by a study procedure or the study infusion, it will be classified as a suspected adverse reaction. If the suspected adverse reaction is unexpected, it will be classified as a serious unexpected suspected adverse reaction (SUSAR).

The VCC will report all unexpected deaths, serious and treatment related adverse events, and SUSARs to the DSMB and sIRB within 7 days after receipt of the report from a clinical site. A written report will be sent to the, DSMB, FDA, and the sIRB within 15 calendar days. The DSMB will also review all reported adverse events and clinical outcomes during scheduled interim analyses. The VCC will distribute the written summary of the DSMB’s periodic review of reported adverse events to the sIRB.

B.1. Unanticipated Problems (UP)

Investigators must also report Unanticipated Problems, regardless of severity, associated with study procedures within 24 hours. An unanticipated problem is defined as follows: any incident, experience, or outcome that meets all the following criteria:

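### The protocol states two different windows for recording unrelated serious adverse events in patients who go home within 72 hours of the infusion: one stops at discharge, the other does not.

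*Protocol*

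**What the plan says.** All of the following is current protocol text.

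**Stops at discharge if that comes before 72 hours**
- Section 12.2, last sentence, on serious events of any cause: collected to study day 4, 72 hours after the infusion ends, "or until hospital discharge, whichever occurs first".
- Section 12.3, opening paragraph, on the investigator's daily determination: "72 hours after completion of the study product infusion, or hospital discharge, whichever occurs first".
- Appendix A, adverse event monitoring on Days 2 to 4, footnote 3: "Only performed if hospitalized".
- Section 5.1, Day 3-8 list: adverse event evaluation runs through Day 4, under a heading that limits the list to inpatients.

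**Runs to 72 hours with no discharge limit**
- Section 12.3, events collected on the case report form: serious events "that are study related (or of uncertain relationship) or occur within 72 hours of the study infusion".
- Section 12.3, Table 4, a row with a 72-hour recording deadline: "Serious, not study related and within 72 hours of infusion".
- Appendix B: "Investigators will report all serious adverse events that occur within 72 hours of study infusion", whether or not they are related.

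**Follow-up after early discharge**
- Section 5.1: "For patients who are discharged prior to Day 4, study personnel will obtain safety outcomes" at the Day 8 telephone call.
- The Day 8 procedure list in 5.1 has clinical status, new medical conditions and vital status, but no adverse event item. Appendix A has no adverse event mark at Day 8.
- Section 7.3.1 has the calls ask about emergency visits, readmissions, date of death and selected non-laboratory safety outcomes.

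**The concern.** The all-cause window exists so that capture of early serious events does not rest on the site's opinion of cause. That is the part stated two ways. A coordinator who learns at the Day 8 call of a serious event on Day 3, after discharge on Day 2, is told by 12.2 that it lies outside collection and by Table 4 that it must be entered.

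The consequence goes beyond form-filling. Under 12.4 the site makes the initial attribution and the independent medical monitor the final one. If a site judges a post-discharge event unrelated and follows 12.2, nothing is entered and the monitor has nothing to review. Appendix B has the DSMB review reported adverse events at the interim analyses, so an event that is not entered does not reach the DSMB by that route either.

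Section 12.2 also sits awkwardly with its own definition. It counts re-hospitalization as a seriousness criterion, yet an unrelated event that begins after discharge and leads to readmission cannot fall inside a window that closed at discharge.

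**Working it through.** There is no figure in the plan to reproduce. The check sets the rules side by side and applies them to one case.

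**Who can be affected.** Study Day 1 is the calendar day of infusion (5.1), so 72 hours, or three days, later falls on Day 1 + 3 = Day 4. The two rules agree for anyone still in hospital at 72 hours and differ only for patients who leave earlier. Exclusion 7 removes patients with a plan for discharge within 24 hours of enrollment. The affected patients are therefore mainly those discharged about 24 to 72 hours after infusion.

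**Worked case.** Discharge at 40 hours after infusion, serious event at 60 hours (40 < 60 < 72).

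| Event at 60 hours | 12.2 collection sentence | 12.3 list and Table 4 | Appendix B |
|---|---|---|---|
| Unrelated, not an exempt study outcome | Outside the window (closed at 40 h) | Collected; recorded within 72 h | Reported |
| Related | Outside the all-cause window, but 12.2 separately requires an alert within 24 h | Collected; recorded within 24 h | Reported within 24 h, whatever the timing |
| Uncertain relationship | Outside the all-cause window | Collected | Reported, as within 72 h of infusion |
| Unrelated study-specific outcome (for example myocardial infarction, pulmonary embolism, unrelated death) | Not applicable | Exempt from adverse event reporting | Exempt (B.3) |

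Reading across:
1. For the unrelated, non-exempt event the instructions are opposite.
2. For related events the requirement to report survives discharge under every section. For events of uncertain relationship, the 12.3 list requires collection explicitly, with no discharge limit.
3. For exempt outcomes the adverse event window does not decide the matter.

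**Where each section falls.** Section 12.3 is on both sides: its opening paragraph stops at discharge, while its list and Table 4 do not. Section 5.1 is mixed: it limits reaction monitoring to the hospital stay, then adds a call for safety outcomes without saying that these include adverse events.

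**Number of events.** This would be (patients discharged before 72 hours) × (rate of unrelated, non-exempt serious events between discharge and 72 hours). The documents give neither term, so no figure can be calculated.

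**The case against.** The strongest reply is that the protocol already covers what matters clinically, and much of it stands.

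- **Delayed reactions.** A reader might infer that a delayed transfusion reaction bringing a patient back within 72 hours could go unreported. The documents do not support this. Such an event would be judged related or of uncertain relationship, and the 12.3 list collects serious events of either kind with no discharge limit. Related ones must be reported within 24 hours.
- **Section 5.1.** A reader might take it as promising full 72-hour adverse event capture. It does not: its monitoring is inpatient, and what it adds is the Day 8 call.
- **No safety contact after discharge.** This is also too strong. Section 7.3.1 already asks about readmissions, emergency visits, death and selected safety outcomes. What is missing is an explicit adverse event item.
- **Surveillance versus reporting.** The 12.3 opening paragraph and the Appendix A row can be read as daily bedside checks, which can end at discharge alongside a duty to report events learned of later. That is a fair reading, and it makes the collection sentence in 12.2 the clearest conflict.
- **Interim stopping.** The stopping rule rests on mortality, which the SAP follows in all locations. Nothing here touches it.

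What the reply does not remove is the 12.2 sentence. It governs collection, not bedside checks, and it contradicts Table 4 and Appendix B. The follow-up call makes it likelier that sites will hear of these events and have to choose a rule.

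**Conclusion.** The contradiction is real and should be resolved. It is limited to serious events judged unrelated, not exempt as study-specific outcomes, and occurring after discharge but within 72 hours of infusion. For these, recording may depend on which section a site follows.

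A reader might go further and conclude that such events will be counted at some sites and missed at others, or that the comparison between arms will be distorted because treatment changes how soon patients leave. The documents show conflicting instructions. They do not show how sites act on them, or any effect of treatment on discharge within 72 hours. Both remain possibilities.

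The number affected is unknown. It is probably small, given the short interval and the two large classes already handled elsewhere. A count of early discharges would not measure it, because that counts patients with a disputed window rather than events, and some Day 4 discharges will already have completed 72 hours.

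The amendment summary gives alignment with the body of the protocol as the reason for revising Appendix B. That suggests a single rule was intended; the discharge cut-off in 12.2 prevents it.

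**What to change.** Reconcile the passages to one data-collection window. The simplest route follows Table 4 and Appendix B:

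1. In the last sentence of 12.2, remove the words "or until hospital discharge, whichever occurs first".
2. In the opening paragraph of 12.3, separate the two duties: daily inpatient checks end at discharge, but serious events are recorded up to 72 hours after infusion wherever the patient is.
3. For patients discharged before Day 4, add an explicit item on adverse events up to 72 hours after infusion to the Day 8 call list in 5.1 and to Appendix A, next to the readmission, emergency visit and safety questions in 7.3.1.

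The cost is wording in four places, one more item on a call that is already made, and a few more unrelated serious events for sites, the coordinating center and the medical monitor to process.
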